5. Medically stable for study participation	Medical history, physical examination and screening laboratory parameters, information from clinical team, review of medical record.
6. Taking an antipsychotic medication other than clozapine at a stable dose for at least 4 weeks	Self report
7. Judged clinically not to be at significant suicide or violence risk.	The Columbia Suicide Severity Rating Scale (C-SSRS); clinical interview
8. Clinically stable for 2 months (CGI \leq 4)	Screening CGI
9. Moderate or lower cognitive disorganization (PANSS P2 \leq 4)	Screening PANSS
10. Visual acuity corrected to at least 20/30	Screening exam
11. An estimated Glomerular Filtration Rate (GFR) \geq 60	Screening labs
12. Fluent English speaker	Screening exam
13. Normal conversational hearing	Screening exam
14. Willing to use qualified methods of contraception for the study duration and up to 2 months after its end	Screening exam

CRITERION	METHOD OF ASCERTAINMENT
Exclusion:	
1. Substance abuse (excluding nicotine) within last 60 days	Physician evaluation/SCID
2. ECG abnormality that is clinically significant in the context of study participation in the opinion of the study cardiologist	ECG
3. Current clozapine use. Clozapine is excluded for two reasons: to avoid the potential confound of treatment resistant patients and because of clozapine's intrinsic NMDA agonist	Self report.

4. Participation in study of investigational medication/device within 4 weeks	Self report
5. Pregnant women or women of child-bearing potential, who are either not surgically-sterile or for outpatients, using appropriate methods of birth control. Women of child-bearing potential must have a negative serum β -hCG pregnancy test at screening.	Instructions to study subject, pregnancy tests as per protocol and review of the medical record.
6. Presence of positive history of unstable significant medical or neurological illness	Medical history and screening labs
7. Positive toxicology screen for any substances of abuse	Urine toxicology screen. Positive tests may be repeated at the discretion of the study investigator for suspected false positive
8. Subjects with suicidal ideation with intent or plan (indicated by affirmative answers to items 4 or 5 of the Suicidal Ideation section of the baseline C-SSRS) in the 6 months prior to screening or subjects who represent a significant risk of suicide in the opinion of the investigator	Screening C-SSRS

Study Procedures

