Provide a clear, concise narrative of study procedures with special attention to the subjects' involvement. Detail the overall study timeline and location of study procedures, list all interventions, assessments and interviews, estimate the duration of each procedure, provide dosing schedules, identify study personnel involved in each procedure, and provide credentials for relevant personnel. For complicated study designs, we strongly encourage attaching tables, flow-charts, and study algorithms.

In the R61, we will confirm target engagement of D-serine + auditory remediation, assess relationships of plasticity changes and cognition, safety and assess the optimal dose of D-serine treatment. In the R33, we conduct a randomized, placebo-controlled, parallel group study with the superior dose of D-serine combined with 16 weekly sessions of the same neuroplasticity-based auditory remediation. The structure of this grant requires successful completion of the R61 phase over 2 years prior to initiation of the R33 phase. We will amend the PSF and consent to include a full description of the R33 phase prior to its initiation.

The study will be conducted in groups of 15 subjects in which 12 subjects will receive D-serine for each of the three treatment visits and 3 will receive placebo for each of the three treatment visits. The first group of 15, will receive 80 mg/kg or placebo, and the second group of 15 subjects will receive 100 mg/kg or placebo, followed by a third group receiving 120 mg/kg or placebo. As previous studies noted minimal carry over effect of D-serine effects ([name] 2010), subjects may be permitted to participate in more than one phase with at least a six

month space in between.

If there are tolerability concerns at the 80 or 100 mg/kg doses, we will add a 60 mg/kg arm, ensuring the assessment of multiple doses. After each cohort, we will obtain permission from both the FDA and the IRB via an amendment, prior to the beginning of the next cohort. We require this safety milestone to be reached in order to begin the next cohort.

R61 Design (Table 1):

R61 Design	Table 1 (R61)	Baseline	Treatment Day			Follow-up ¹
			1	2	3	
		Day -30 to -1	Day 1	Day 8±2	Day 15±2	
	Consent	x				
	Medical screening	x				
	D-serine/Placebo		x	x	x	
	MMN		x	x	x	
	Auditory Remediation/EEG		x	x	x	
	Cognitive and behavioral ratings	x				
	Clinical laboratory/pregnancy/vitals	x	x	x	x	x
	SAFTEE/C-SSRS	x	x	x	x	x
	1. If necessary to follow-up any abnormalities.					

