Interviews and neuropsychological assessments are associated with minimal risk. Some participants may find the interviews and assessments tiring or distressing. Risks are to be minimized by allowing as much flexibility in the interview process (e.g., doing the interview in several meetings, giving breaks) as possible. If subjects have emotional responses, appropriate psychological support is given. Most patients find the interviews and assessments helpful.

Pregnant or Nursing Females

We will not administer experimental medication to pregnant females. For these reasons, pregnant females are excluded from the study. All female patients will demonstrate a negative urine human chorionic gonadotropin (HCG) test prior to sessions to confirm that the patient is not pregnant.

Emergencies

If, during the course of interviewing and assessment procedures, study staff identifies a condition that mandates immediate clinical intervention or official reporting (e.g., homicidality/suicidality), all necessary steps will be taken, and

the emergency procedures of the Division of Experimental Therapeutics, inpatient unit NKI, and the Lieber Clinic will be followed. In the case that staff determine that the participant is at significant risk for self or other destructive behavior, any mental health professional currently treating the participant will be contacted and necessary treatment steps will be taken (e.g., hospitalization, continuous observation, referral to a care provider, etc.). All patients will be given numbers to call in the event of an emergency during treatment: the primary phone number of the treating clinician and the number for the Lieber clinic (both the front desk number and the number for the Doctor- on-call beeper). If the treating clinician, a covering MD in the Lieber clinic, NKI, or the Doctor- on- Call is immediately unavailable, the subject will be instructed to not delay and to go to their nearest Emergency Room.

COVID-19 risks

Going out in public and traveling involves some risk of infection with COVID-19. There is risk of COVID-19 infection during in-office visits and during travel for research purposes.

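### The risk section's heading names nursing women, but no criterion in the eligibility table shown excludes them

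*Protocol*

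**What the plan says.** Two parts of the Protocol bear on this point.

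- **Risks/Discomforts/Inconveniences.** One subsection is headed "Pregnant or Nursing Females". Its dosing rule is "We will not administer experimental medication to pregnant females" and its eligibility statement is "For these reasons, pregnant females are excluded from the study". It then requires a negative urine hCG test before sessions.
- **Inclusion/Exclusion Criteria.** Exclusion 5 is "Pregnant women or women of child-bearing potential, who are either not surgically-sterile or for outpatients, using appropriate methods of birth control". Its second sentence requires women of child-bearing potential to have a negative serum pregnancy test at screening. The method of ascertainment is "Instructions to study subject, pregnancy tests as per protocol and review of the medical record". Inclusion 14 is "Willing to use qualified methods of contraception for the study duration and up to 2 months after its end".

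Study Procedures adds a urine pregnancy test for women able to conceive before each dose. Criteria for Early Discontinuation stops study drug on a positive urine pregnancy test. In the text supplied, the subsection heading is the only place in either document where nursing is mentioned.

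**The concern.** The heading announces two groups and the text beneath it gives a rule for one. Site staff decide eligibility from the numbered table, so a group that the protocol itself sets beside pregnant women has no written rule there. A pregnancy test does not detect lactation, so the scheduled tests do not fill the gap.

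What is at stake is participant protection. The Protocol describes this as the first use of weekly D-serine above 60 mg/kg, and its safety summary counts 16 earlier patients at 120 mg/kg. No study in its renal safety table is described as including nursing women. The study runs at two sites, and without a written rule each could decide differently about the same patient.

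**Working it through.** The plan gives no figure to reproduce. The check is to take a nursing woman through the table.

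**Step 1. Count.** There are 14 inclusion and 8 exclusion criteria: 14 + 8 = 22. Criteria naming nursing, lactation or breastfeeding: 0 of 22.

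**Step 2. Could another criterion exclude her indirectly?**
- Inclusion 5 (medical stability) and exclusion 6 (unstable medical or neurological illness): nursing is not an illness, so a healthy nursing woman passes both.
- Inclusion 14 (contraception): she can meet it.
- Exclusion 5, second sentence: she meets it with a negative serum test.
- The remaining criteria concern diagnosis, cognition, medication, substance use, suicide risk, renal function, ECG, hearing, vision and the like. None bears on nursing.

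**Step 3. Read exclusion 5 both ways**, because its first sentence is garbled.
- *Intended reading.* Women of child-bearing potential are barred unless they are surgically sterile or use contraception. Three places support this: the second sentence of exclusion 5 sets a test for such women, inclusion 14 asks for contraception, and Study Procedures tests women able to conceive before each dose. On this reading a nursing woman with a negative test who uses contraception is eligible.
- *Literal reading.* The words can bar any woman of child-bearing potential who is not surgically sterile. The nursing women who remain eligible are then mainly those who are surgically sterile.

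The gap exists on both readings and is much narrower on the literal one.

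**Step 4. How many people?** The documents do not give the number of nursing women, nor the expected share of women. The preliminary study described in the Background had 21 patients, 90% men, aged 44.0±11.5. If R61 recruited the same mix (an assumption), 0.10 × 45 = 4.5 of the 45 would be women. With 30% or 50% women the figures are 13.5 and 22.5. These are counts of all women aged 18 to 50. The number nursing would be a small part of them, quite possibly none.

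**Step 5. Is one question at screening enough?** From the earliest screening day (Day −30) to Day 1 is 30 days with no Day 0, or 31 under the stated 31-day screening period. From Day 1 to the latest planned third dose (Day 15 + 2 = Day 17) is 16 days. The total is 46 to 47 days. The renal hold-and-repeat rules could delay a dose, so this is not a firm maximum. Even so, a woman who is neither nursing nor pregnant at screening will not ordinarily begin nursing within a period of that order.

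**The case against.** The case for leaving this alone has four parts.

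- **Exclusion 5 is wider than pregnancy.** This stands. A reader might infer from the risk section that the table bars pregnant women and nobody else, or that applying it to the letter would admit nursing women generally. The text does not support either. Exclusion 5 also reaches a class of women of child-bearing potential, and read literally it would turn away most nursing women. The broader gap depends on the intended reading, which is well supported but is still an interpretation.
- **The intent is unclear.** This stands in part. No sentence says that nursing women are to be excluded, and the only sign of it is one word in a heading. The mismatch could be settled by excluding them or by removing the word. Some edit is needed in either case.
- **The rule may exist elsewhere.** This stands as a limit. The consent pages were removed, the instructions to subjects are not reproduced, and the main grant, to which the Protocol refers for D-serine safety, is not supplied. The point therefore concerns the table and text shown.
- **Nursing would come to light anyway.** Medical history, physical examination, record review and contact with outside providers before randomisation make unnoticed enrolment unlikely. They do not tell staff what to do once they know.

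**Conclusion.** The point holds as a low-severity, precautionary correction to the eligibility wording: the heading names nursing women, the two rules beneath it do not, and 0 of 22 criteria exclude them. Few or no participants are likely to be affected.

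It should not be read as a demonstrated hazard. The documents give no lactation risk data. Nor do the dosing figures measure the problem. In each planned cohort "12 subjects will receive D-serine for each of the three treatment visits and 3 will receive placebo for each of the three treatment visits", which is a 12/15 = 80% chance of active drug, and three doses come to 3 × 80 = 240 up to 3 × 120 = 360 mg/kg. Those figures apply to any participant assigned as planned and say nothing about how often a nursing woman would enrol.

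No defect is claimed in the pregnancy testing or the stopping rule. No estimate, endpoint, dose decision or go/no-go criterion changes, and the SAP is untouched. The conclusion rests on the eligibility table as supplied and, for its wider form, on the intended reading of exclusion 5.

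**What to change.** - Begin exclusion 5 with 'Pregnant or breastfeeding women'.
- Ascertain breastfeeding by self-report at screening. Ask it afresh for each enrolment, because Study Procedures lets a subject take part again after at least six months.
- Add nursing women to the dosing sentence and the exclusion sentence in the risk subsection, so that heading and rule agree.
- If the sponsor intends nursing women to be eligible, say so and remove the word from the heading.

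No extra checks at dosing visits and no new stopping rule are needed. The cost is one phrase, two matching sentences and one screening question. The protocol already requires FDA and IRB permission by amendment between cohorts, so the edit can go with one of those submissions. The downside is at most a very small loss of eligible patients.

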After a negative urine pregnancy test for fecund women and the Columbia Suicide Severity Rating Scale (C-SSRS), each visit will begin with a pretreatment EEG/capping. Subjects will then receive D-serine or placebo. Auditory remediation will begin 30 minutes after study drug administration, to allow for training during peak D-serine levels ([name], Malhotra et al. 2010). EEG will be recorded during sessions, to assess theta-ITC and secondary EEG measures. Immediately after auditory remediation, subjects will complete post treatment MMN. A D-serine level will be drawn immediately after the session using established methods to allow for functional pharmacodynamics readout, along with urinalysis and clinical laboratory assessments. The SAFTEE will be used to assess general side effects. Columbia/NKI EEG labs are both under the supervision of Drs. [name] and [name] and have previously conducted parallel studies, ensuring cross-site validation.

Study drug and maintenance of the blind: D-Serine and placebo will be administered as a solution, prepared (premixed) in water and prescribed only as “study medication.” D-serine will be dosed by weight (e.g. 80 mg/kg

for the 1st cohort). Study medication will be dispensed to subjects in individual, identical appearing bottles, and dispensed on the day of the session by an un-blinded pharmacist otherwise uninvolved in the study. As previously, D-serine will be obtained from Evonik, and an artificial sweetener will be used as placebo.

The un-blinded pharmacist, based upon predetermined assignment schedule, will make study assignment. Envelopes containing treatment assignment will be kept in pharmacy and in patients' clinical charts. Envelopes will be unsealed only in cases of medical necessity. Blind-breaks will be on individual subject basis only. The pharmacist does not participate in assessing any dependent variable and conveys no information about drug status to patients or staff except in a medical emergency.

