The PI has an active IND for D-serine (122821), specifically permitting use up to 120 mg/kg in this protocol.

D-serine is a naturally occurring amino acid that is present in high concentrations in the human brain. D-serine is cleared almost exclusively by the kidney.

The primary safety concern of D-serine is the potential for nephrotoxicity. Nephrotoxicity is a theoretical concern during D-serine treatment, as rats receiving D-serine experience a reversible acute tubular necrosis. When present, this toxicity leads to high levels of glucose and protein being present in the urine. This effect, however appears to be isolated to rats, in that other rodent species (e.g., mice) do not show similar sensitivity to D-serine, nor is toxicity observed in non-rodent species (e.g., rabbit, dog, monkey)²¹⁹. Further, toxic effects of D-serine, even in rats, are fully reversible even with continued D-serine treatment. The specific sensitivity of rats appears to be due to the presence of a D-serine transporter in rat kidney that actively reabsorbs D-serine from the urine, leading to buildup of high levels within the rat kidney. The presence of this transport mechanism is apparent from the low levels of D-serine in rat urine relative to that of other species, despite relatively similar serum levels.

In humans, there is no evidence of reabsorption of D-serine by the kidney. The safety of high dose D-serine in non-rat animal species has been further established as part of the safety reports provided to the FDA for my IND.

14 human trials have been published with D-serine (Table), including 431 subjects and treatment duration up to 16 weeks of daily dosing. 102 subjects received high dose (>30 mg/kg), including 16 patients at 120 mg/kg. Across all of the studies, only one subject was reported to have abnormal renal values related to D-serine treatment. The abnormality occurred in a subject receiving 4 weeks of the 120 mg/kg dose. Even at that dose, the abnormality was extremely mild in that it involved only an increase in protein (2+ by dipstick) without accompanying increase in glycosuria or change in creatinine level. The abnormal urinalysis values were observed 4 weeks following treatment onset, and fully resolved within a few days of stopping treatment.

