Dose escalation plan: *This study has a built-in space between doses, maximizing safety. Furthermore, no side effects were noted in our prior, once weekly intermittent treatment study.* For the present study, potential nephrotoxicity will be monitored through serum chemistry and urine microscopic examination looking for evidence of active sediment (e.g. casts), proteinuria or glycosuria after each dose, as per FDA suggestions. No subjects with baseline renal impairment, as evidenced by a GFR<60 or clinically abnormal laboratories will be enrolled in the study. As attached, FDA has approved our IND, which incorporates the monitoring procedures described above as well as a sequential dose escalation to identify the maximum tolerated dose.

Placebo

The primary risk with placebo is that patients' symptoms may get worse or may not improve. Since patients will remain on their antipsychotic, and the risk of placebo is small.

Potential subjects will be informed about the results of previous studies and will be encouraged to seek treatment outside of the study as an alternative to study participation if they wish.

Antipsychotics:

All subjects will be asked to remain on their pre-study antipsychotics during the study, and any dose changes for this 6 week study, if any, will be included as co-variables for analysis

EEG Recordings

These studies entail the recording of EEG from the scalp employing standard sensors and amplification methods. These procedures are well standardized and there are few known risks. These are principally due to equipment malfunction. The recording equipment used in these studies meet the current design criteria for subject safety, including isolation from potential electrical hazards. Regular preventative maintenance and careful attention to recording procedures further minimize the already insignificant risks of electrophysiological recording. Electrodes and materials used for affixing them in place are kept scrupulously clean and sterilized and materials are utilized which minimize the chance of skin and scalp irritation. Urine pregnancy tests will be conducted at the time of EEG on all female patients to confirm that the patient is not pregnant prior to study drug administration.

Interviews and Neuropsychological Assessments

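### No safety assessment is scheduled for every subject after the day of dose 3, although Aim 1 and the gate between cohorts rely on the safety record

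*Protocol*

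**What the plan says.** Protocol, Study Procedures, Table 1 (R61 Design): laboratory tests, pregnancy test and vital signs form one row, and SAFTEE and C-SSRS another. Both rows are marked at baseline, on the three treatment days (Day 1, Day 8±2, Day 15±2) and in the Follow-up column. The footnote to that column reads "If necessary to follow-up any abnormalities".

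The description of the visits in the same section gives the order within a treatment day. The C-SSRS is completed before dosing. "Auditory remediation will begin 30 minutes after study drug administration". After the session a D-serine level is "drawn immediately after the session using established methods to allow for functional pharmacodynamics readout, along with urinalysis and clinical laboratory assessments". The SAFTEE is to be used, but its time within the visit is not given.

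Criteria for Early Discontinuation requires urinalysis at every visit and repeat testing for creatinine, cast, protein and glucose abnormalities. Where these lead to discontinuation, testing continues until two clear results.

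The Dose escalation plan (under Risks) describes serum chemistry and urine microscopy "looking for evidence of active sediment (e.g. casts), proteinuria or glycosuria after each dose, as per FDA suggestions".

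Safety is then relied on in two places. Aim #1 hypothesises that D-serine will be safe. Before each higher-dose cohort, Study Procedures requires FDA and IRB permission and adds: "We require this safety milestone to be reached in order to begin the next cohort".

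**The concern.** The schedule treats the last dose differently from the first two. After doses 1 and 2 every subject returns about a week later, and an event in the interval can be recorded then. After dose 3 a return depends on there being an abnormality to follow. In a subject who looked well on Day 15, a later adverse event, change in suicidality or renal change is recorded only if someone reports it or it comes to light by another route.

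The safety statement is at stake. Nephrotoxicity is the protocol's stated primary concern, and the decision to open the next dose level refers to a safety milestone. If a cohort is summarised as free of events, a reader will assume that all three doses were observed in the same way. For the third dose, no delayed event may mean only that none was looked for.

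**Working it through.** **1. What follows each dose, for every subject, in the R61**

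| Assessment | Dosing day | After doses 1 and 2 | After dose 3 |
|---|---|---|---|
| Blood and urine tests | After the session | Next visit, 7±2 days later, drawn after the next dose | Only if triggered |
| SAFTEE | Yes, time within visit not stated | Next visit | Only if triggered |
| C-SSRS | Before dosing | Next visit, before the next dose | Only if triggered |

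For the C-SSRS, the assessment on the day of dose 3 precedes that dose, so none is scheduled after it.

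**2. Doses affected**

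Inputs: 12 active and 3 placebo subjects per cohort, three doses each, three cohorts (Study Procedures; SAP, R61 Component). Full enrolment, completion of all doses and no added 60 mg/kg arm are assumed.

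- Active doses per cohort: 12 × 3 = 36.
- Followed by a scheduled later visit: 12 × 2 = 24.
- Not followed by one: 12, and 12/36 = 33%.
- Over three cohorts: 3 × 36 = 108 active doses, of which 3 × 12 = 36 are third doses.
- Placebo third doses in the same position: 3 × 3 = 9. Contacts needed to cover everyone: 36 + 9 = 45.

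**3. Length of observation**

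The last scheduled safety sample falls between Day 15 − 2 = 13 and Day 15 + 2 = 17.

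**4. Can a rate be attached?**

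The protocol's renal table sums to 102 subjects above 30 mg/kg and 329 at or near 30 mg/kg, together 431, as stated. Its one renal case gives 1/431 = 0.23% overall and 1/16 = 6.25% at 120 mg/kg, which agree with the stated 0.2% and 6.3%. The case arose under daily dosing: "The abnormal urinalysis values were observed 4 weeks following treatment onset". Neither figure is a rate of delayed events after a weekly dose, and the documents contain no such rate. The gap can be sized in doses, not in missed events.

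**5. Do other provisions close it?**

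Updates to community providers (Coordination with outside providers) and the free treatment offered after the study (Research Related Delay to Treatment) are not described as safety data collection. They may bring an event to light, but they do not replace a scheduled assessment.

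**The case against.** The case for the plan is substantial, and most of it stands.

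- **Dose 3 is observed.** Laboratory tests and the SAFTEE are scheduled on that day, and renal abnormalities are retested. A reader might infer that the third dose is never followed. The documents do not support that; what is missing is a routine check after the dosing day in subjects whose results were normal.
- **The footnote does not bar late reports.** It does not say that the abnormality must have been found at a visit, so an event reported after Day 15 could trigger follow-up. Such events are not routinely sought, but they are not unobservable.
- **The Dose escalation plan is not contradicted.** Same-day sampling after the session is monitoring after each dose. The protocol says that its monitoring procedures are part of the approved IND.
- **The renal case does not show delayed onset.** It was found after four weeks of daily treatment and resolved within days of stopping. The earlier weekly study (21 patients, 60 mg/kg, three weekly sessions) lists no renal abnormality, though at a lower dose.
- **The milestone's content is not in these documents.** Milestone detail is referred to the main application, so the data behind each escalation request are unknown here.

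A reader might also be tempted by a detection calculation. With a 1/16 risk per subject, 12 subjects give 1 − (15/16)^12 = 54% for at least one case. Counting only two thirds of that risk as observable gives 1 − (1 − (2/3)/16)^12 = 40%. The arithmetic is right, but the comparison is unsupported. The rate comes from daily dosing at 120 mg/kg, the last planned dose level, so it describes neither planned step up from 80 or 100 mg/kg. The difference also depends wholly on assuming that events are invisible on the dosing day and spread evenly over doses. Nor can one say that per-dose event rates are biased, since no passage available here plans such a rate.

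None of this supplies a scheduled assessment after the day of dose 3. FDA and IRB review can use only what was collected.

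**Conclusion.** The point holds as a cheap improvement to the plan. For 12 of 36 active doses per cohort (36 of 108 overall), observation scheduled for every subject ends on the dosing day. For the C-SSRS it ends before the dose. Delayed adverse events, changes in suicidality and renal changes after dose 3 are not routinely sought in subjects with normal Day 15 results, while Aim #1 and the cohort milestone speak of safety without that limit.

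The conclusion rests on Table 1 and the visit description as written, and on the assumption that the main application adds no routine contact after dose 3. The dose counts assume full enrolment and completion. No probability of missing an event is claimed. The documents do not show that any delayed event occurred or is likely, or that the monitoring breaches what was agreed under the IND.

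**What to change.** Reconcile the Table 1 footnote with Aim #1 and the cohort safety milestone in one of two ways.

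1. **Apply the SAFTEE and C-SSRS already marked in the Follow-up column to every subject after dose 3, by remote contact.** Include the results in each cohort's safety summary. The protocol already provides for remote visits by video, telephone and web (Methods to Protect Confidentiality), and remote contact respects its COVID-19 limit on on-site attendance. Cost: a protocol amendment and one remote contact per subject, at most 45.
2. **If follow-up stays conditional, say so wherever safety is summarised.** State that safety after dose 3 was observed on the dosing day only, apart from triggered follow-up, and that no C-SSRS was scheduled after that dose. Cost: wording only.

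Whether and when later renal tests are taken cannot be settled remotely and is a matter of clinical monitoring. That decision belongs to the sponsor, FDA and IRB; the plan should record what they decide.
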